To apply the results obtained in Primary Aim 1 to build (1) an intervention made up of only active components and (2) if necessary, a second intervention that is optimized for scalability. Intervention (1) will be made up of the best set of components and component levels, based on the results of the experiment conducted in Primary Aim 1. Our conversations with private insurers suggest that in order to be scalable, Opt-IN needs to be implementable for \$500 or less. If Intervention (1) exceeds an estimated cost of \$500, we will identify the combination of components and component levels corresponding to the largest treatment effect that can be obtained for implementation costs of \$500 or less. This will be the new Opt-IN intervention.

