5. Buddy Training. Social support is a well-documented correlate of successful health behavior change, prompting numerous efforts to harness peers as treatment agents. Engaging peers together in treatment groups has augmented weight loss (Wadden et al., 2011), and training peers to be supportive has yielded varying degrees of improved health behavior change (Gruder et al., 1993; Hogan et al., 2002; May & West, 2000; Katula et al., 2011). While we find it unrealistic to expect all individuals to have a buddy able to attend in-person groups, pilot data from ENGAGED indicate that 100% of participants can identify a support person from either their local or virtual environment. All buddies will first receive a document with information on how to provide support for his/her friend or family member after consenting to participate. The chosen support person for those randomized to receive buddy training will be coached further on how to provide support for his/her friend. Training will occur via one individual telephone coaching session, followed by four online webinar lessons; two of the webinars will be "core" sessions focusing on an introduction to healthy weight loss and how to be a supportive buddy, while the remaining two webinars will comprise additional relevant support topics (e.g., dealing with difficult situations or plateaus). Each webinar will last approximately 30-45 minutes. These trainings will be delivered quarterly, and content will be adapted from existing curricula (Nettles & Belton, 2010; West et al., 1998). Each webinar will comprise didactics followed by a group supervision for buddies. Supervision will involve shared problem solving about challenges in supporting participants. Buddies who are randomized to a condition requiring training and webinar participation will receive a \$5 online gift card after attending each required webinar, and will have the opportunity to receive an additional \$20 gift card if they attend 3 or 4 of the 4 required webinars.

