4.3.2 Intervention Component Cost Estimation

Table 2 shows the estimated cost of implementing the CORE, plus the cost of the low and high

Table 2- Estimated Cost of Lowest vs. Highest Level of Intervention Components		
Intervention Component Levels	Cost/person Lowest Level	Cost/person Highest Level
1. Phone Sessions: 12 or 24	\$86.52	\$173.04
2. PCP: no reports or reports	\$0	\$34.88
3. Texts: no or yes	\$0	\$0
4. Meal Replacements: no or yes	\$0	\$29.96
5. Buddy Training: no or yes	\$0	\$68.82
+. Core intervention cost	\$281.67	\$281.67
	Minimum cost \$ 368.19	Maximum cost \$588.37

levels of each supplemental intervention component. The CORE infrastructure that makes the intervention accessible to all participants involves a: (a) web portal on a server; (b) Smartphone application. The web portal will house a series of interactive lessons that can be assigned as 24 single lessons or as 12 pairs. The portal also receives weight, diet, and physical activity data transmitted by the patient. Uploaded data and information about lesson access and completion

are conveyed to coaches via a web interface. The Opt-IN Smartphone application, originally developed for ENGAGED, transmits dietary intake and physical activity data to the portal. To estimate the cost of implementing the intervention, we assume that all components of the system are fully developed. Two main implementation costs remain: 1) \$70 annual fee to access the study's web infrastructure, including the CalorieKing food database, interactive lessons, and coach interface; 2) technical support, estimated at 20% effort for a technician with an annual salary of approximately \$65k/year. We estimate the cost of maintenance per person to be $(\$65k * .20 \text{ effort}) / 150 \text{ participants/year} = \$86.67/\text{person}$. Thus, the total cost of the CORE is $\$70 + \$125 + \$86.67 = \$281.67/\text{person}$.

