(1) Telephone Coaching session cost was estimated assuming that a health educator salaried at \$30,000 year (\$14.42/hour) offered 12 [$14.42 * 0.5 * 12 = \$86.52/\text{person}$] or 24 [$14.42 * 0.5 * 24 = \$173.04/\text{person}$] sessions (up to 20 minutes of phone coaching, plus 5-minutes to prep for the call by reviewing notes, plus 5 minutes to record notes after the call). (2) PCP Reports. Half of the participants will have two reports of their weight loss progress sent to their PCP (at 3-months, and 6-months), as per Appel et al. (2011). Direct costs of sending these reports is for staff salary to generate and print reports and cover letters and obtain signatures ($\$30 \times 1 = \$30/\text{person}$), and for postage stamps ($\$0.44 \times 2 = \$0.88/\text{person}$). Indirect costs will cover the printing and stationary ($\$2 \times 2 = \$4/\text{person}$). Total cost: $\$34.88/\text{person}$. (3) Text Messaging. That half of the sample randomized to text messaging will receive automated texts seven times per week. Text messages will be sent from a computer terminal that permits us to send texts for free through the Opt-IN application. (4) Meal Replacement. Those recommended to use meal replacement products will be given a one-week supply of Slim Fast or similar meal replacement product (14 shakes and 14 bars). $14 \text{ shakes} * \$1.35/\text{shake} + 14 * \$0.79/\text{bar} = \$29.96/\text{person}$. (5) Buddy Training. Project staff will perform the training. After an initial individual telephone training for those randomized into a Buddy Training condition, further training and supervision will occur via group phone calls/webinars. Every six weeks, study coordinators will offer the training at a variety of times/dates. Four different webinar topics will be offered to accommodate new buddies just joining the trial. Estimated staffing cost per person for this training is $\$28.82/\text{person}$: 45 minutes for initial training + 1.25 hours for 3 shared 1-hour group teleconferences). Buddies randomized to receive additional training and webinars will receive \$5 online gift cards after completion of each webinar, and an additional \$20 online gift card for completing at least 3 of the 4 webinars. Total cost of buddy training is $\$68.82/\text{person}$.

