4.4 Intervention

A. Behavioral Coaching and Curriculum. Treatment will be delivered as 24 online lessons supplemented by individual telephone coaching. All participants will be given the goal of 7% weight loss via calorie reduction from usual intake and increased physical activity. A login to a website will be provided, where participants will be able to access online interactive lessons. Lessons topics, shown in Appendix, will be based on the DPP and Look AHEAD (e.g., self-monitoring, portion size estimation, fat and calorie content of foods, meal and snack patterning, becoming active, stimulus control). Telephone coaching sessions will last approximately 10-15 minutes. At the beginning of each coaching call, coaches will confirm with the participant that they consented or did not consent for the telephone coaching session to be audio recorded, based on what they indicated on the study consent form. Coaches will discuss that week's lesson materials, recapping the main points. The phone session will also include feedback on self-monitoring and goal attainment (observed from uploaded diet and activity data), problem solving about barriers, and motivational interviewing.

B. Dietary Intervention. During the initial baseline assessment, per DPP, participants will receive both a calorie goal and a fat goal (based on 25% of total daily calories from fat). Those weighing 120 to 174 lb at baseline will be instructed to follow a 1200-kcal/d diet (33 grams fat);

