Primary Aim 2 is to make decisions about intervention components and component levels based on the factorial experiment results. We propose to use a modified version of a decision making approach frequently used in engineering (Wu & Hamada, 2000), which emphasizes main effects, using interactions as additional valuable information. This emphasis is consistent with our objective of identifying a set of components and component levels in which each component is making a detectable contribution to the overall effect, and any inactive components have been eliminated. We remind the reader that the mixed model analysis will be performed using effect coding, which will keep any covariances among main effects and interactions to a minimum. This makes it reasonable to start the decision making process by examining main effects, and then to consider interactions carefully in subsequent steps in the process. (Recall that our theoretical model does not predict any substantially-sized higher-order interactions, which is the basis for selection of the highly economical fractional factorial design. This Resolution V design enables examination of all two-way interactions.) The decision making process can be summarized as follows: Step 1: Initial tentative selection of components and component levels, consisting of identification of the components that show a significant main effect on the primary outcome variable, weight. If buddy training, recommended meal replacements, texting, or PCP report have a significant main effect, they will tentatively be selected for inclusion in the intervention. If there is a significant positive main effect of Number of Phone Coaching sessions, this is evidence that the more expensive level (24 sessions) performs better than the less expensive level (12 sessions), so it should be selected; otherwise, the less expensive level should be selected. Step 2: Consideration of interactions and final decision. Next we will examine interactions to look for any indication that we should consider reversing a decision made in Step 1. For example, suppose both Texting and PCP Report have significant main effects, so they were tentatively selected in Step 1. If there is a significant negative interaction between them, this means that the combined effect of Texting and PCP Report is less than the sum of the main effects. Suppose Texting has the larger main effect of the two. In that case we will start from the premise that Texting is selected, and then pose this question: When Texting is selected, *does PCP Report have a large enough incremental effect to justify its selection?* This question can be addressed by examining the simple effect of PCP Report when Texting is at the Yes level. Similar decision making logic will be used to examine all significant interactions that involve any components selected in Step 1 to arrive at the final decisions about selection of components and component levels. Step 3: Identifying the combination of components and levels that produces the largest effect that can be obtained for \$500 or less. If the costs associated with the combination of component and component levels selected in the process described above exceeds the upper limit of \$500, it will be necessary to consider less expensive versions of the intervention. Using as a starting point the set of components and component levels selected in Step 2, we will examine various scenarios in which we remove Yes/No components and change the levels of Either/Or components, and compute the expected outcome based on the regression parameters obtained in the statistical analysis to select the one with the largest expected effect that can be delivered for under \$500.

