7.1 Study Timeline

The study time line and randomization goals appear in Table 6. As shown, quarters 1, 2, and 3 will be dedicated to completing development of the protocol and study tools. Development activities include completing programming of the Opt-IN app for usability across all Smartphone platforms, programming online lessons, developing and programming algorithms needed to generate session guides, assessments and reports, preparing treatment manuals and fidelity check protocols, and training coaching staff. Recruitment, screening, and randomization activities will commence in Year 1, quarter 4 and continue through Quarter 1 of Year 5. The remainder of Year 5 is for final follow-up, data analyses and report writing.

	Quarter 1 Sept - Nov	Quarter 2 Dec-Feb	Quarter 3 Mar-May	Quarter 4 June-Aug	Total
Year 1	Development				
Year 2	Testing / 15	47	45	45	(152)
Year 3	45	45	45	45	(182)
Year 4	45	45	45	45	(182)
Year 5	44	Data analysis, report writing			(44)
					N=560

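### The unit costs behind the $500 rule do not match the intervention described, and for some component selections the differences change which package is eligible

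*Combined protocol and SAP*

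**What the plan says.** Section 1.4 (Primary Aim 2) sets the target: the combination giving the "largest treatment effect that can be obtained for implementation costs of \$500 or less". Section 5, Primary Aim 2, Step 3 applies it. If the package chosen in Steps 1 and 2 costs more than $500, cheaper versions are compared, in order to "select the one with the largest expected effect that can be delivered for under" $500.

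The costs come from Table 2 and the text of section 4.3.2:

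- **Buddy training, $68.82.** Staff time is 45 minutes of initial training plus "1.25 hours for 3 shared 1-hour group teleconferences". Gift cards are $5 for each webinar plus $20 for completing at least 3 of 4. Section 3.2.1 describes the training differently: "Training will occur via one individual telephone coaching session, followed by four online webinar lessons", each lasting about 30-45 minutes. Section 4.3.1 gives the same number and length.
- **Coaching, $86.52 or $173.04.** Each call is costed at "up to 20 minutes of phone coaching" plus 10 minutes for preparation and notes. Section 4.4 says "Telephone coaching sessions will last approximately 10-15 minutes".
- **CORE, $281.67.** The text announces two remaining costs: a $70 annual fee, and "technical support, estimated at 20% effort for a technician" spread over 150 participants a year ($86.67). The sum then printed is $70 + $125 + $86.67.

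**The concern.** Step 3 is a hard threshold that can remove a component already shown to work. Suppose PCP reports, meal replacements and buddy training have significant main effects and 24 calls do not. Unless an interaction reverses a choice at Step 2, the selection is then 12 calls plus those three components, with or without texts, which cost nothing. On the printed costs this misses the cap by $1.85, and Step 3 would call for a cheaper version. Several inputs to that total are uncertain by more than $1.85.

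I found no statement of when the cost inputs are fixed. If they are reconciled only after the component effects are known, the choice of call length, webinar hours or volume could settle which package is named Opt-IN.

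**Working it through.** **Reproducing Table 2** (inputs from section 4.3.2)

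- CORE: 70 + 125 + (65,000 × 0.20)/150 = 70 + 125 + 86.67 = $281.67.
- Calls: 14.42 × 0.5 × 12 = $86.52; 14.42 × 0.5 × 24 = $173.04.
- PCP reports: 30 + 0.88 + 4 = $34.88.
- Meal replacements: 14 × 1.35 + 14 × 0.79 = $29.96.
- Buddy training: 14.42 × (0.75 + 1.25) + 4 × 5 + 20 = $68.84, against the printed $68.82. The 2 cents are immaterial, and I use $68.82.
- Minimum: 281.67 + 86.52 = $368.19. Maximum: 281.67 + 173.04 + 34.88 + 29.96 + 68.82 = $588.37. Both agree with Table 2.

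**Packages against the cap as printed**

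Texts are free, so there are 2 × 2 × 2 × 2 = 16 packages with distinct contents other than texts. Twelve calls plus everything is 281.67 + 86.52 + 34.88 + 0 + 29.96 + 68.82 = **$501.85**. The other five over $500 all have 24 calls: with PCP + meal ($519.55), buddy ($523.53), meal + buddy ($553.49), PCP + buddy ($558.41), and all ($588.37). Ten are eligible.

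**Changing one input at a time**

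- *Webinars.* The plan does not show how 1.25 hours per person was obtained. I assume that staff time scales with total webinar hours, so one webinar hour costs 14.42 × 1.25/3 = $6.01 per person. Four 1-hour webinars add $6.01; four of 45 minutes make 3 hours, as costed; four of 30 minutes make 2 hours and save $6.01.
- *Calls.* A 15-minute call takes 25 minutes in all: 14.42 × 25/60 × 12 = $72.10, a saving of $14.42 on 12 calls and $28.84 on 24. A 10-minute call takes 20 minutes: $57.68, a saving of $28.84 and $57.68.
- *Volume.* Break-even for 12 calls plus everything is 13,000/(86.67 − 1.85) = 153.3 a year, so 154 is enough.
- *The $125.* Removing it gives a CORE of $156.67 and a maximum of 588.37 − 125 = $463.37.

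| Input changed | 12 calls + all | Eligible of 16 |
|---|---|---|
| None (as printed) | $501.85 | 10 |
| Four 1-hour webinars | $507.86 | 10 |
| Four 45-minute webinars | $501.85 | 10 |
| Four 30-minute webinars | $495.84 | 11 |
| 15-minute calls | $487.43 | 13 |
| 10-minute calls | $473.01 | 14 |
| 152 a year | $500.71 | 10 |
| 154 a year | $499.60 | 11 |
| $125 removed | $376.85 | 16 |

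Starting from $68.84 for buddy training, the second row is $507.88; its eligible count is unchanged.

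**In combination.** Four 1-hour webinars move nothing alone, but can once calls are shorter. At 15 minutes, 24 calls + buddy goes from 523.53 − 28.84 = $494.69 to $500.70. At 10 minutes, 24 calls + meal + buddy goes from 553.49 − 57.68 = $495.81 to $501.82.

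**The case against.** Much of the case on the other side stands.

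- **Webinar count.** Three against four does little alone. At one hour each, the 12-call full package is over the cap before and after; at 45 minutes the cost is unchanged. Only the 30-minute end changes a result by itself.
- **Call length.** Up to 20 minutes is a ceiling and 10-15 minutes a typical length, so both can be true. Costing at the ceiling is conservative. Against a cap, however, it works in one direction: it excludes packages that the described call length would admit.
- **Volume.** A reader might set 150 a year against the timetable in section 7.1 ("The study time line and randomization goals appear in Table 6"), which shows 182 in each of Years 3 and 4, and infer a contradiction. The documents do not support that. The 150 belongs to the cost of implementing a fully developed system, not to trial accrual, and Year 2 is 152. What remains is that 150 has no stated basis and that break-even lies very close to it.
- **Reach of the rule.** A reader might infer that these differences decide Step 3. They do not in general: Step 3 runs only if Steps 1 and 2 select a package over $500. With the $125 kept, ten of the 16 packages are under the cap on every input tried, and 24 calls plus everything is over on every one.
- **Standing of the near-cap package.** It is tempting to call 12 calls plus everything the result that the protocol most hopes for. Section 3.2.1 expects added components to bolster 12 sessions, but the stated aim is to drop inactive components, and no section states a preference for keeping all of them.

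**Conclusion.** The concern holds in limited form. Table 2 adds up, but its inputs do not agree with the intervention described, and they differ by more than the $1.85 that separates one plausible selection from eligibility. They can change the final package for some Step 1-2 outcomes and leave it untouched for others.

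The unexplained $125 matters most: with it, six packages exceed the cap as printed; without it, none does and Step 3 never applies. Call length comes next, moving three packages (15 minutes) or four (10 minutes) under the cap. Webinar number and length move at most one package when changed alone.

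The webinar figures rest on staff time scaling with webinar hours. The call figures keep the 10 minutes of preparation and notes. The $125 may be a real cost whose description was lost; the documents do not say.

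**What to change.** Before outcome data are opened:

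1. Reconcile section 4.3.2 with sections 3.2.1, 4.3.1 and 4.4, so that Table 2 costs the number and length of webinars and the call time that will be delivered. Show how staff hours per buddy are derived.
2. Say what the $125 in CORE pays for, or remove it.
3. State the basis for 150 participants a year.
4. Add to Step 3 that it will be run on this fixed table, and that a sensitivity analysis will report whether the selected package changes at the low and high ends of these inputs.

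The $500 cap remains the sponsor's choice and need not be softened. The cost is a revised table and a sentence or two in section 5; no additional participant data are needed.

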4.4 Intervention

A. Behavioral Coaching and Curriculum. Treatment will be delivered as 24 online lessons supplemented by individual telephone coaching. All participants will be given the goal of 7% weight loss via calorie reduction from usual intake and increased physical activity. A login to a website will be provided, where participants will be able to access online interactive lessons. Lessons topics, shown in Appendix, will be based on the DPP and Look AHEAD (e.g., self-monitoring, portion size estimation, fat and calorie content of foods, meal and snack patterning, becoming active, stimulus control). Telephone coaching sessions will last approximately 10-15 minutes. At the beginning of each coaching call, coaches will confirm with the participant that they consented or did not consent for the telephone coaching session to be audio recorded, based on what they indicated on the study consent form. Coaches will discuss that week's lesson materials, recapping the main points. The phone session will also include feedback on self-monitoring and goal attainment (observed from uploaded diet and activity data), problem solving about barriers, and motivational interviewing.

B. Dietary Intervention. During the initial baseline assessment, per DPP, participants will receive both a calorie goal and a fat goal (based on 25% of total daily calories from fat). Those weighing 120 to 174 lb at baseline will be instructed to follow a 1200-kcal/d diet (33 grams fat);

participants weighing 175 to 219 lb will be advised to follow a 1500-kcal/d diet (42 grams fat); those 220 to 249 lb will be asked to follow an 1800-kcal/d diet (50 grams fat); and those over 250 lb will be instructed to follow a 2000-kcal/d diet (55 grams fat). Coaching provides feedback and advice on participants' self-monitoring and, when the participant has provided data, on diet and activity. Coaches discuss periods of apparent non-recording or nonsubmission of records. When the participant has supplied data, the coach reviews the foods that supplied the highest calorie and fat intake for the past week, notes any unusual features of meal or activity timing (e.g., skipped meals, night eating, long periods of inactivity), reviews fruit/vegetable, fiber and protein intakes, and develops a collaborative action plan. Frequently recommended dietary strategies include portion control, use of lower-calorie substitutes, increased intake (within calorie allowance) of fruits and vegetables, or (per randomization) use of meal replacement products. Coaches will monitor participants to ensure a safe rate of weight loss. If weight loss equals or exceeds 3 pounds/week for 4 consecutive weeks, the patient's calorie intake goal will be increased in 250 kcal increments until the goal of 1-2 lb/week weight loss has been achieved. For participants who request coach help because their weight appears non-responsive despite self-reported adherence to energy goals, a strategy for absence of weight loss is planned. Because under-reporting of energy intake is prevalent among overweight individuals, the coach will first address the diet documentation process (i.e., portion size estimation, omissions). If participants do not lose weight for two consecutive weeks, the calorie goal will be further reduced by 250 kcal increments toward an intake level that yields an average 1-2 lb weight loss per week. No patient's calorie goal will be set below 1200 kcal per day.

C. Physical Activity Intervention. Participants will be encouraged to engage in a variety of safe physical activities classified as moderate intensity by the Compendium of Physical Activities. Participants will be encouraged to self-monitor moderate intensity physical activity on the smartphone application. Physical activity goals will gradually increase number of minutes of moderate intensity activity needed to meet activity adherence criteria each week as follows: weeks 1-4 (100 minutes/week), 5-8 (150 minutes/week), 9-12 (200 minutes/week), 13-16 (250 minutes/week), and 17-24 (300 minutes/week).

D. Supplemental Intervention Components. Participants randomized to text messaging will receive text messages written by the Opt-IN team. The content of the texts will be responsive to participants' stated preferences as well as to their uploads. Texts will include positive feedback and encouragement as well as suggestions for change. Participants will have the opportunity to pick from different "schedules" of text messages (e.g., one text a day, every day; 2 texts per day, 3 days a week), but all participants randomized to text messaging will receive a minimum of 7 texts per week to distinguish them from non-texting participants. Participants will also have the opportunity to "step-up" these 7 text messages with an additional 2 "general information" texts per week. All texting participants may also receive general (mass) texts about holidays or weight management during special occasions.

For those randomized to have a report of their weight loss progress sent to their PCP, a report with cover letter will be mailed quarterly to both participant and provider, briefly explaining the study, graphing the patient's weight loss and providing several behavioral recommendations to support weight loss (Appel et al., 2011). Reports will be tailored to those participants that have lost no weight, lost a little weight, or have met the weight loss goal at that assessment point (i.e., 3.5% or more lost at 3-months, or 7% or more lost at 6-months).

All buddies (regardless of condition) will receive an e-mailed explanation of the study with a document about how to best support their friend or family member; they will first undergo a consent process by telephone. For those randomized to the buddy training condition, the buddy will receive an individual phone training session and participate in 4 webinars using gotomeeting.com. Buddies will choose a nickname and will be advised to use only this nickname and to only refer to their buddy as "My Buddy" to preserve confidentiality during group webinar/teleconferences.

Those participants randomized to receive 12 coaching telephone calls will review the A and B pair of lessons for each assignment, whereas those randomized to receive 24 calls will review A and B lessons as separate assignments.

Those randomized to meal replacements will receive their week's supply of meal replacements (14 shakes and 14 snack bars) at the time of their in-person Randomization session visit.

